9.1 General Considerations

For quantitative variables, all summaries will include the sample size, mean, median, standard deviation, minimum, and maximum. For the qualitative variables, the summaries will include the number and percentage of subjects for each outcome.

Nominal p-values and confidence intervals will be presented to aid in interpretation of the summary of data.

SAS® (version 9.2) will be used for generation of analyses.

9.2 **Primary Endpoint(s)**

The number and percentage of subjects with each category of the Aronchick scale will be displayed by treatment group, overall and by age group. In addition, the number and percentage of subjects classified as a responder (Excellent or Good rating) will be included in the summary. Specifically, for the overall summaries, the Prepopik 1 sachet and the standard of care groups for the two age groups will be combined; and, all Prepopik groups will be combined.

The treatment group difference will be assessed by constructing the 90% and 95% confidence intervals (CIs) of the difference in proportions between each Prepopik group and standard of care within each age group. Additionally, the 90% and 95% CIs of the difference in proportions between the following combined groups will be constructed:

- Prepopik 1 sachet versus combined standard of care
- All Prepopik groups combined versus combined standard of care

The 90% and 95% confidence intervals will be multiplied by 100 so as to present the resulting interval as percentages.

The analyses will be performed for the ITT and PP populations. The ITT population is the primary population and the PP population is supportive.

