# 9.6.2 Primary Efficacy Endpoint

The primary efficacy endpoint will be the proportion of subjects classified as success defined by excellent or good in the Aronchick scale. The primary efficacy analysis will be based on the ITT dataset.

The proportion will be presented by treatment group within each age group, for all Prepopik 1 sachet groups combined, for all Prepopik groups combined, and all standard of care groups combined with the 95% confidence interval.

The treatment group difference will be assessed by constructing the 95% confidence interval of the difference in proportion between each Prepopik group and standard of care within each age group, all Prepopik 1 sachet groups combined and all standard of care groups combined, and all Prepopik groups combined and all standard of care groups combined.

The analyses will be conducted for the PP populations as well.

Trial Code: 000103 Date: 28-Jul-2014 E-Protocol Amendment-18395; Ver. 5

> Supersedes: 4 Page 47 of 65

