3.2 Determination of Sample Size

Approximately 6-8 sites in the US are planned. A sufficient number of subjects will be screened to ensure up to approximately 75 (~15 subjects per treatment arm).

A total of at least 45 subjects will be exposed to Prepopik. In the two Phase 3 studies for adults, 83% and 84.2% of subjects were classified as success after bowel preparation with Prepopik. With 45 subjects, if 80% of subjects are classified as success in this study, the exact 95% confidence interval of the success rate will be calculated as 65% - 90%.

4 Subject Disposition

All subjects screened will be accounted for. The number of subjects screened but not randomized/allocated to treatment will be presented with the reason(s) for screen failure in a data listing.

The number and percentage of subjects randomized, beginning treatment, having a colonoscopy, completing, and withdrawing from the study will be tabulated for each treatment group, overall and by age group. The denominator for the percentages is the total number of subjects in the given treatment group, or the combined sample as appropriate. Reasons for early withdrawal will be tabulated by treatment group. Individual subject listings of study completion information will be produced, including the reason for early withdrawal.

The number of subjects included and excluded from safety and efficacy populations will be summarized for each treatment group. In addition, the reason(s) for exclusion from each population will be summarized. Individual subject listings of reasons for exclusion from the analysis populations will be produced. In addition, a separate subject listing of any eligibility violations will be produced.

The number and percentage of subjects randomized, treated, completing/withdrawing from the study and included/excluded from safety and efficacy populations will also be tabulated by study site.

5 **Protocol Deviations**

Major and minor protocol deviations will be defined and documented prior to database lock. Major protocol deviations which exclude the subject from the PP analysis set will include the following:

- Key violations of the protocol inclusion or exclusion criteria
- Significant violation of the dosing regimen as recorded on the eCRF including the amount of study preparation, and timing of receiving study medication
- Receiving study medication other than randomized assignment

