9.3 Secondary Endpoint(s)

The following secondary endpoints will be summarized in the same manner as the primary endpoint:

- proportion of subjects who completed colon cleansing
- proportion of subjects who completed the colonoscopy procedure
- proportion of subjects with responses to the individual questions on the Tolerability and Satisfaction Questionnaire

Additionally, based on the individual questions subjects responses will be categorized as tolerable and as satisfactory according to the following algorithms:

- Tolerable is defined as a response of 1 (Never) or 2 (Rarely) to the five items specified in question 3.
- Satisfactory is defined as a response of 1(Very Easy) or 2 (Easy) on question 1 and a response of 1 (Very Well) or 2 (Well) on question 2.

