10.5 Physical Examination

The number and percentage of subjects having an abnormal physical exam at Screening, or with a change from Screening, will be summarized by body system for each treatment group, overall and by age group.

Physical examination findings at each evaluation will be listed for the safety dataset. Subjects with abnormal findings will be noted on the data listings.

11 Interim Analyses

No interim analyses are planned for this study.

12 Deviations from Protocol Analysis

The following are a list of changes and/or additions from the protocol specified analyses:

- In addition to the pre-specified 95% CIs, 90% CIs will also be computed and displayed.
- Additional summaries for pre-specified orthostatic changes in blood pressure will be provided.
- Pharmacokinetic concentration summaries and listings will be provided.

13 References

[1] Clinical Practice Guideline: Orthostatic vital sings full version. Emergency Nurses Association. December 2011.

14 Tables, Listings and Figures

The document with tables, listings, and figures (TLF) shells is presented in a separate document.

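### Has the SAP dropped the 95% confidence intervals that the protocol requires for each success proportion?

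*SAP*

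**What the plan says.** Protocol 9.6.2, repeated in the synopsis, makes two requests for the primary endpoint. The first is the success proportion by treatment group within each age group, for the 1 sachet groups combined, "for all Prepopik groups combined, and all standard of care groups combined with the 95% confidence interval". The second, in its own paragraph, is a 95% interval for each difference from standard of care.

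SAP 9.2 covers the first request with a count and a percentage: "the number and percentage of subjects classified as a responder (Excellent or Good rating) will be included in the summary". For the second it is explicit about "constructing the 90% and 95% confidence intervals (CIs) of the difference in proportions between each Prepopik group and standard of care within each age group", and it adds two combined comparisons at the same two levels.

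Three other places in the SAP bear on the point:

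- SAP 9.1, directly above 9.2: "Nominal p-values and confidence intervals will be presented to aid in interpretation of the summary of data".
- SAP 12, which lists changes and additions relative to the protocol's analyses: "In addition to the pre-specified 95% CIs, 90% CIs will also be computed and displayed". The other two items are orthostatic summaries and pharmacokinetic concentration summaries and listings.
- SAP 3.2, matching protocol 9.1: with 45 subjects and 80% success, "the exact 95% confidence interval of the success rate will be calculated as 65% - 90" (per cent).

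For the secondary proportions, SAP 9.3 says: "The following secondary endpoints will be summarized in the same manner as the primary endpoint". Protocol 9.6.3 uses the same formula. The table shells are in a separate document.

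**The concern.** The primary objective is descriptive, with standard of care as a reference group. No hypothesis is tested against a margin and no power is calculated. The single-group success proportion is therefore a main result, and its interval conveys how precisely it is known. The only justification for the sample size is such an interval, for all Prepopik subjects pooled. Yet SAP 9.2 gives intervals for differences and none for the proportions themselves, and SAP 12 does not record that anything was left out.

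If the SAP were the only instruction to the programmer, the precision that the trial was sized to deliver might not appear in the primary efficacy table. The secondary proportions, which follow the primary endpoint's format, would lose theirs too. The interval method would also be chosen after the data were seen. With about 15 children per arm, that choice visibly moves the limits.

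**Working it through.** **Step 1. Count what is affected.** From protocol Table 3-1 and section 9.6.2:

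- Proportions: 3 arms at 9-12 years + 2 arms at 13-16 years + 1 sachet combined + all Prepopik + all standard of care = 8.
- Differences: 2 at 9-12 years + 1 at 13-16 years + 2 combined = 5.

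SAP 9.2 names intervals for the 5 differences and for none of the 8 proportions. The silence is real.

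**Step 2. Reproduce the plan's own figure.** Inputs from SAP 3.2 and protocol 9.1: n = 45 and 80% success, so x = 0.80 × 45 = 36. The exact (Clopper-Pearson) 95% limits are beta quantiles:

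- lower = B(0.025; x, n − x + 1) = B(0.025; 36, 10) = 65.4%
- upper = B(0.975; x + 1, n − x) = B(0.975; 37, 9) = 90.4%

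These round to the stated 65% and 90%. The Wilson interval for the same data, with z = 1.96, is [p + z²/2n ± z√(p(1 − p)/n + z²/4n²)] / (1 + z²/n):

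- centre = (0.8 + 0.0427) / 1.0854 = 0.7764
- half-width = 1.96 × √(0.003556 + 0.000474) / 1.0854 = 0.1146
- limits 66.2% to 89.1%, which do not round to the stated figure

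The documents' word exact is therefore meant literally, and it names the method for the pooled estimate.

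**Step 3. How much an unstated method could matter.** The same 80% is used in each group purely as an illustration.

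| n | x | Exact 95% CI | Wilson 95% CI | Shift in lower limit |
|---|---|---|---|---|
| 15 | 12 | 51.9% to 95.7% | 54.8% to 93.0% | 2.9 points |
| 30 | 24 | 61.4% to 92.3% | 62.7% to 90.5% | 1.3 points |
| 45 | 36 | 65.4% to 90.4% | 66.2% to 89.1% | 0.8 points |

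At n = 15 either interval spans roughly 40 points (95.7 − 51.9 = 43.8 exact; 93.0 − 54.8 = 38.2 Wilson). Both tell the reader the same thing: one arm on its own is imprecise.

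**Step 4. Is the requirement still in force?** Set the texts side by side.

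- Protocol 9.6.2 and the synopsis require the intervals and fix the level at 95%.
- SAP 12 is the place for departures from that. It contains three items, all additions. Its first item treats the 95% intervals as already specified and puts 90% intervals alongside them.
- SAP 9.1 says confidence intervals will accompany the summaries.
- Nothing in either document withdraws the single-group intervals.

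Read together, the documents still call for the eight intervals at 95%. The missing words in SAP 9.2 are an unrepeated phrase.

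**Step 5. What the reader would lose in the worst case.** Suppose the table showed only the count and percentage. Steps 2 and 3 use nothing but x and n, both of which SAP 9.2 reports for every group, so each interval can be computed from the published table.

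**The case for a change.** The strongest reply is that a SAP should be sufficient on its own. SAP 9.1 speaks of confidence intervals in general but names no quantity, level or method. It nearly repeats protocol 9.6.1, and the protocol still needed 9.6.2 to say which intervals were wanted. The sample-size sentence is planning text, not an analysis instruction. SAP 12 also leaves open whether the added 90% level applies to single proportions. With arms of 15, a simple Wald interval for 12/15 runs from 59.8% to 100.2%: its lower limit lies nearly 8 points above the exact one, and its upper limit is impossible.

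Part of this stands. SAP 9.2 does not restate the requirement, and neither document names a method in its analysis section. Three things limit it.

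- The 95% level is fixed in the protocol, so only the method is open.
- The spread between methods does not measure the omission. Protocol 9.6.2 names no method either, so copying its sentence into SAP 9.2 word for word would leave that spread unchanged. SAP 9.2 likewise names no method for the differences.
- No document proposes a Wald interval. The only method either document mentions for a success rate is the exact one, and an analyst working from SAP 3.2 would use it.

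The point about secondary proportions is weaker still, because protocol 9.6.3 refers back to a primary analysis that includes the intervals.

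**Conclusion.** The wording gap is real, but it calls for no change to the plan. Eight single-group 95% intervals are required by protocol 9.6.2, are not repeated in SAP 9.2, and are not withdrawn anywhere. An analyst who reads the two documents together would produce them, and SAP 3.2 points to the exact method. Writing the phrase into SAP 9.2 would restate an existing obligation. It would not alter any estimate, comparison, success criterion or sample size: the p-values are nominal and no decision rule rests on these intervals.

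The residual uncertainty is the choice of a reasonable method, worth about 0.8 points on the lower limit for the pooled Prepopik rate and 2.9 points for one arm, at an illustrative 80% success and the planned group sizes.

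This conclusion assumes that the protocol governs where the SAP is silent and SAP 12 lists no departure. The table shells, which were not available, may already show the intervals; the conclusion does not depend on that, because the counts are reported in any case.

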#### **NUMBER OF SUBJECTS**

A sufficient number of subjects will be screened to ensure up to approximately 75 (for 9-12 years old, 15 subjects for the Prepopik ½ sachet x2, the Prepopik 1 sachet x2, and standard of care group; for 13-16 years old, 15 subjects for the Prepopik 1 sachet x2 and standard of care). For PK sampling, approximately 5 subjects per treatment group (a total of 15, 5 aged 13-16 years and 10 aged 9-12 years) will be assessed.

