#### 3 INVESTIGATIONAL PLAN

### 3.1 Overall Trial Design

This study is a randomized, assessor-blind, multicenter, dose-ranging study. Subjects undergoing an elective complete colonoscopy will randomly receive one of the following products:

- "Split Dose" Prepopik: 2 divided doses given the night before (first dose) and approximately 5 hours prior (second dose) to procedure. A dose is defined for one subset of subjects aged 9 years to 12 years as ½ sachet, for another subset of subjects aged 9 years to 12 years per randomization as 1 sachet and for subjects aged 13 to 16 years as 1 sachet. For "Day Before" Prepopik and fluids see Section 5.
- Oral PEG based preparation/local standard of care per appropriate label and/or institutional instructions.

Table 3-1 Overview of Study Treatment Groups by Age

	Age	Age Group		
Treatment Group	9-12 years	13-16 years	Total	
Prepopik: ½ sachet	15	0	15	
Prepopik: 1 sachet	15	15	30	
Standard of care	15	15	30	
Total subjects	45	30	75	

Pediatric subjects requiring colonoscopy, who fulfill all screening criteria, and sign an informed consent and assent (as required), will be randomized. One of the treatment arm products will be provided to the subject in a randomized fashion. The designated unblinded coordinator will instruct the subject and his/her parent/guardian on the use of the bowel preparation, and along with the subject and his/her parent/guardian, will sign a nondisclosure affidavit form (APPENDIX 1), which will prevent the subject and the unblinded coordinator from disclosing the bowel preparation treatment the subject used. Treatment will be blinded to the endoscopist and his/her assistant(s) assessing the efficacy of the 2 tested preparations when local or institutional methods are used. Their dosage timing and diet will be captured in the data. This approach had been used successfully in the Prepopik adult trials.

Colon cleansing will be performed using Prepopik for oral administration or oral PEG based preparation/local standard of care for oral solution.

Trial Code: 000103 Date: 28-Jul-2014 E-Protocol Amendment-18395; Ver. 5 Supersedes: 4

Page 20 of 65

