#### 4.2.2 Randomization

At a clinic visit preceding the colonoscopy (Visit 2), eligible pediatric subjects will be randomized to one of the treatment arms by the age group. Subjects aged 9 years to 12 years will be randomized to Prepopik ½ sachet x2, Prepopik 1 sachet x2, or standard of care in 1:1:1 ratio. Subjects aged 13 years to 16 years will be randomized to Prepopik 1 sachet x2 or oral PEG based preparation/standard of care in 1:1 ratio. Randomization numbers will be allocated sequentially to the subjects at each site. This will occur in the order in which the subjects are enrolled.

Under no circumstances will subjects enrolled in the study be permitted to re-enroll for a second time in this study.

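### The pooled all-Prepopik versus standard-of-care difference mixes age strata allocated 2:1 and 1:1 without stratification, so at the planned counts one sixth of any age gap in success shows as a treatment difference

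*SAP*

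**What the plan says.** Protocol 4.2.2 randomises within age group. Ages 9-12 go to Prepopik ½ sachet x2, Prepopik 1 sachet x2 "or standard of care in 1:1:1 ratio"; ages 13-16 go to Prepopik 1 sachet x2 or "oral PEG based preparation/standard of care in 1:1 ratio". The counts are in Protocol Table 3-1 ("Overview of Study Treatment Groups by Age") and the synopsis: 15 per arm, so three arms of 15 in the younger group and two in the older ("for 13-16 years old, 15 subjects for the Prepopik 1 sachet x2 and standard of care"). SAP 3.1 calls the design age-stratified.

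For the overall summaries, SAP 9.2 states that "the Prepopik 1 sachet and the standard of care groups for the two age groups will be combined", and that all Prepopik groups are combined too. It then plans 90% and 95% intervals for two pooled differences in proportions: Prepopik 1 sachet against combined standard of care, and "All Prepopik groups combined versus combined standard of care". Protocol 9.6.2 likewise presents pooled proportions for "all Prepopik groups combined, and all standard of care groups combined", and plans a 95% interval for their difference.

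Neither document gives stratum weights, a stratified estimator or an age-adjusted model for the pooled differences. SAP section 12, which lists departures from the protocol analysis, adds none. The method of constructing the interval is not named. SAP 9.3 extends the approach: "The following secondary endpoints will be summarized in the same manner as the primary endpoint".

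**The concern.** Combining the arms across age groups and taking one difference compares two groups with different age mixes. The imbalance comes from the allocation, because the younger stratum has two Prepopik arms and the older has one. It is therefore expected whenever the trial runs to plan, and is not a chance imbalance that averages out.

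If children of 9-12 and 13-16 differ in how well they cleanse, part of that difference is reported as a treatment difference, with a sign set by whichever age group does better. At stake is the one between-group summary that uses all 75 subjects, in a trial whose primary objective covers ages 9-16 with standard of care as the reference. That line could contradict the within-age results in the same table. The completion and questionnaire proportions in SAP 9.3 inherit the problem.

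**Working it through.** **The plan's own figure.** SAP 3.2 and Protocol 9.1 give an exact 95% interval of 65%-90% for 80% success in 45 subjects. The Clopper-Pearson interval for 36/45 is 65.4% to 90.4%, so the figure reproduces. It is a single-arm precision statement and does not depend on the point below.

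**Inputs (Protocol Table 3-1 and 4.2.2).** Ages 9-12: 15 + 15 = 30 Prepopik, 15 standard of care. Ages 13-16: 15 and 15.

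**Age mix of the pooled arms.** Share aged 9-12:
- all Prepopik: 30/45 = 2/3
- combined standard of care: 15/30 = 1/2
- difference: 2/3 - 1/2 = 1/6

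**What the crude difference estimates.** Let p be success on Prepopik and s success on standard of care, with subscripts y (9-12) and o (13-16). The crude difference has expectation

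(2/3 p_y + 1/3 p_o) - (1/2 s_y + 1/2 s_o) = [2/3 (p_y - s_y) + 1/3 (p_o - s_o)] + 1/6 (s_y - s_o).

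The bracket is a weighted average of the two within-age effects. The last term is purely age mix and remains when both effects are zero. For an age gap of 10, 20 or 30 points it is 1.7, 3.3 or 5.0 points.

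**Worked example with no effect in either age group.** Ages 9-12: 24/30 vs 12/15 (80% each). Ages 13-16: 9/15 vs 9/15 (60% each). Pooled: 33/45 vs 21/30 = 73.3% vs 70.0%, a difference of +3.3 points (Wald 95% interval -17.5 to +24.2).

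**Behaviour of the crude interval with no treatment effect.** Exact binomial enumeration at the planned counts, unpooled Wald 95% interval. The success rates by age are assumptions, because the documents give none.

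| Success 9-12 / 13-16 | Mean difference (points) | SD | Mean half-width (points) | Interval above 0 | Interval below 0 | Total |
|---|---|---|---|---|---|---|
| 0.80 / 0.80 | 0.0 | 0.094 | 18.1 | 2.5% | 3.4% | 5.8% |
| 0.90 / 0.80 | +1.7 | 0.082 | 15.8 | 3.2% | 2.4% | 5.6% |
| 0.90 / 0.70 | +3.3 | 0.089 | 17.6 | 4.7% | 1.3% | 6.0% |
| 0.70 / 0.90 | -3.3 | 0.094 | 18.6 | 0.9% | 5.9% | 6.8% |
| 0.90 / 0.60 | +5.0 | 0.093 | 19.1 | 6.2% | 0.7% | 6.9% |
| 0.60 / 0.90 | -5.0 | 0.099 | 20.2 | 0.5% | 6.7% | 7.2% |

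The SAP's 90% interval at 0.90/0.70 lies above / below zero in 8.9% / 2.9% (total 11.8%, the same as with no gap). The main effect is to move error into one tail.

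**With stratification.** Mantel-Haenszel weights are 30 x 15/45 = 10 and 15 x 15/30 = 7.5, that is 0.57 : 0.43. The stratified difference has mean 0.0 in every scenario. Its SD is 0.090 against 0.089 for the crude difference at 0.90/0.70, and 0.096 against 0.094 at 0.80/0.80. A stratified Wald interval at 0.90/0.70 lies above / below zero in 2.7% / 3.7% (total 6.4%). The tilt due to age mix has gone, but the small-sample error of the Wald form remains.

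**The other pooled contrast.** Prepopik 1 sachet against combined standard of care has younger shares of 15/30 and 15/30. The gap is 0, so there is no such bias at the planned counts.

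**The case against.** The strongest reply concerns weight, since the arithmetic is not in dispute. The objective is descriptive, standard of care is a reference group, p-values and intervals are nominal, and sample size rests on single-arm precision; no test, margin or success rule uses this interval. One of five planned contrasts is affected, and the within-age rates and differences are reported beside it, so an attentive reader could see the discrepancy. The age gap is assumed: at 10 points the bias is 1.7 points against a half-width of 15.8, with tails only mildly tilted, and a clear tilt needs gaps of 20 to 30 points. The stratified Wald interval does not lower total error (6.4% against 6.0% at 0.90/0.70), and no operating characteristics are available here for a score-type interval. Even when stratified, the contrast averages two doses in the younger group and one in the older.

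Two further qualifications concern scope. One sixth is exact only at the planned counts, whereas enrolment is approximate, so the factor will move with realised and per-protocol numbers. Crude pooling is inferred from the word combined; the interval method is unnamed and the table shells are in a separate document.

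All of this limits the importance of the point, and the mixed-dose limitation remains after the fix. None of it removes the bias. Showing the within-age results makes a discrepancy visible but leaves the pooled figure uncorrected. If a stratified estimator was intended, the SAP needs to say so.

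**Conclusion.** The point holds and should be fixed. Read plainly, the pooled all-Prepopik difference is confounded with age by design, by one sixth of the age gap in success at the planned counts: 1.7 to 5.0 points for assumed gaps of 10 to 30 points, in either direction. This is small beside the interval's half-width of about 16 to 20 points and changes total error little; it mainly shifts error into one tail. No formal decision rests on it.

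The conclusion assumes Table 3-1 enrolment and a crude difference. With a real treatment effect, the relevant age gap is the one on standard of care. The within-age contrasts are unaffected, and the pooled 1-sachet contrast is balanced as planned. The bias is known before any data are seen and can be removed at almost no cost, which is why a modest effect in a descriptive trial still merits the change.

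**What to change.** In SAP 9.2, and in Protocol 9.6.2 for consistency, state that the all-Prepopik versus combined standard of care difference is an age-stratified risk difference over the two randomisation strata. Mantel-Haenszel weights are one option; other stratum weights stated in advance would also remove the confounding. Name the interval method. A stratified score-type interval is suggested because the Wald form keeps its small-sample error at these counts. Label the crude pooled percentages as descriptive only.

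Apply the same rule to the secondary proportions in SAP 9.3. For the pooled 1-sachet contrast it is optional, for consistency and to guard against imbalance in realised or per-protocol numbers.

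The cost is one sentence in the SAP and a few lines of code, with no extra subjects or data. The standard error rises by about 1% (0.090/0.089 = 1.01 at 0.90/0.70).
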